6.6.4. Vital Signs

Vital sign parameters will be listed. All other vital signs collected during the course of the study will be considered source data only and will not be required to be reported on the CRF. Vital signs associated with AEs may be collected in the CRF.

6.6.5. Electrocardiograms

Triplicate ECGs were required at each assessment. A mean score is calculated for any replicate measurements having the same nominal visit. The mean measurement is reported.

ECG summaries will include all ECG assessments from the on-treatment period. All ECG assessments will be listed, and those collected outside the on-treatment period will be flagged in the listing.

The analysis of QT data is complicated by the fact that the QT interval is highly correlated with heart rate. Because of this correlation, formulas are routinely used to obtain a corrected value, denoted QTc, which is independent of heart rate. This QTc interval is intended to represent the QT interval at a standardized heart rate.

Fridericia's correction (QTcF) will be programmatically derived using the following formula:

$$QTcF(\text{msec}) = QT(\text{msec}) / \sqrt[3]{RR(\text{sec})}$$

and Bazett's correction (QTcB) will be programmatically derived using the following formula:

$$QTcB(\text{msec}) = \frac{QT(\text{msec})}{\sqrt{RR(\text{sec})}},$$

where RR represents the RR interval of the ECG, in seconds.

The correlation between RR and QTcF will be explored graphically. If these are correlated and there are a sufficient number of participants (eg, >30) with baseline ECGs, a study specific correction (QTcS) will be performed as follows:

- b will be estimated from $\ln(QT) = a + b * \ln(RR)$;
- and QTcS will be derived as $QTcS = QT(\text{msec}) / (RR(\text{sec}))^{1/b}$.

Data will be summarized using QTcB and QTcF. However, if these are not appropriate for the data set due to an observed large correlation between corrected QT and HR using the baseline assessments, the results will also be summarized using QTcS.

QT, heart rate, QTcB and QTcF will be summarized using simple descriptive statistics (mean, standard deviation, median, quartiles, minimum, and maximum) of actual values and change from baseline for each nominal visit over time (ie, unscheduled assessments will be excluded). The total number of participants for change from baseline will include all participants in the treatment arm who have both a baseline and a value at the nominal visit. Baseline will be selected as defined in [Section 3.4](#).

The mean absolute QTc, QTcB, QTcF, RR, PR, and QRS will be presented with two-sided 95% confidence intervals and the baseline adjusted mean QTc, QTcB, QTcF, RR, PR, and QRS will be presented with two-sided 90% confidence intervals.

Additionally QTcB and QTcF (and QTcS if applicable) will be summarized by maximum on-treatment values using the following categories:

- ≤ 450 msec;
- > 450 msec but ≤ 480 msec;
- > 480 msec but ≤ 500 msec; and
- > 500 msec.

Unscheduled assessments will be utilized in addition to planned assessments.

Shift tables will be provided for baseline value versus worst on-treatment value.

Additionally maximum increases from baseline (including scheduled and unscheduled assessments) will be summarized based on the following categories:

- Change >60 msec;
- Change >30 msec but ≤ 60 msec; and
- Change ≤ 30 msec.

If more than one ECG is measured at a nominal time post-dose (eg, triplicate ECGs within 2-4 minutes), the mean will be used to represent a single observation per participant and time post-dose. If any of the three individual ECGs results in a QTc ≥ 500 msec and the mean is not ≥ 500 msec, then that participant's data will be described in the safety section in the study report in order to place the ≥ 500 msec value in appropriate clinical context. On the other hand, such individual ≥ 500 msec value within a triplicate will not be included in the categorical analysis unless the average from that triplicate is also ≥ 500 msec. Data listings will contain the means from a triplicate as well as the parameters from each of the three ECGs. Note that using the mean value may result in a participant having a measurement that is not represented by an actual ECG.

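### The study-specific QT correction divides by RR^(1/b) where its own regression calls for RR^b, so QTcS would be badly wrong at almost any heart rate other than 60 bpm

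*SAP*

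**What the plan says.** SAP 6.6.5 explains that "formulas are routinely used to obtain a corrected value, denoted QTc, which is independent of heart rate". It gives two fixed corrections: Fridericia, QT over the cube root of RR ("QTcF(\text{msec}) = QT(\text{msec}) / \sqrt[3]{RR(\text{sec"), and Bazett, QT over the square root of RR ("QTcB(\text{msec}) = \frac{QT(\text{msec})}{\sqrt{RR(\text{sec"), "where RR represents the RR interval of the ECG, in seconds".

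It then adds a conditional third correction, which depends on a graphical look at RR against QTcF: "If these are correlated and there are a sufficient number of participants (eg, >30) with baseline ECGs, a study specific correction (QTcS) will be performed". The two steps are:

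- "b will be estimated from $\ln(QT) = a + b * \ln(RR", so b is the slope of ln(QT) on ln(RR);
- "QTcS will be derived as $QTcS = QT(\text{msec}) / (RR(\text{sec}))^{1/b", so QT is divided by RR raised to 1/b.

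QTcB and QTcF are always summarised. QTcS is added if a large correlation with heart rate remains at baseline. On the categorical table the section says: "Additionally QTcB and QTcF (and QTcS if applicable) will be summarized by maximum on-treatment values". The categories are ≤450, >450 to 480, >480 to 500 and >500 msec. No other part of the SAP restates or corrects the QTcS formula. The protocol gives no formula for this study; it mentions QTcS only when describing earlier results (section 2.2.2.1.3.5).

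**The concern.** The two steps do not fit together. A slope b from the log-log regression has to be used as the exponent itself, not as its reciprocal. The reciprocal would be right only if b were a root index (about 3, as in a cube root) or the slope of ln(RR) on ln(QT), and the SAP defines b as neither.

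The formula is prespecified, so a programmer who follows it exactly produces wrong numbers. QTcS exists for the case where QTcF and QTcB leave heart-rate dependence behind. As written it would put back far more dependence than it removes: faster rates would appear as values above 500 msec, and slow rates would pull prolonged values down. The protocol reports a positive correlation between QTc and drug concentration in earlier work and lists QT abnormalities among its adverse events of special interest, so readers will look at these tables.

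**Working it through.** **Inputs from SAP 6.6.5.** The regression ln(QT) = a + b·ln(RR); the formula QTcS = QT/RR^(1/b); QTcF = QT/RR^(1/3); QTcB = QT/RR^(1/2); RR in seconds, so RR = 60/HR. The documents state no value of b and no QTcS result, so there is no printed figure to reproduce.

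**Assumed inputs.** b from 0.25 to 0.50, and the QT and heart-rate values shown below.

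**Step 1, algebra.** The regression gives QT = e^a · RR^b.

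- Dividing by RR^b leaves e^a, which is free of RR.
- Dividing by RR^(1/b) leaves e^a · RR^(b − 1/b). The remaining log-log slope on RR is b − 1/b, which is zero only if b = 1 or −1.

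For b = 0.25, 1/3, 0.40 and 0.50 that slope is −3.75, −2.67, −2.10 and −1.50. Uncorrected QT has slope b. The written formula therefore reverses the sign and enlarges the dependence, by a factor of 3.75/0.25 = 15 at b = 0.25 and 1.50/0.50 = 3 at b = 0.50.

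**Step 2, check against the SAP's own corrections.** With b = 1/3, QT/RR^b is QTcF exactly, while QT/RR^(1/b) is QT/RR^3. With b = 1/2, QT/RR^b is QTcB exactly, while QT/RR^(1/b) is QT/RR^2.

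**Step 3, single readings with b = 0.33 (1/b = 3.03).**

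| HR (bpm) | RR (s) | QT (msec) | QT/RR^b | QT/RR^(1/b), as written |
|---|---|---|---|---|
| 100 | 0.6 | 340 | 402 | 1,599 |
| 75 | 0.8 | 370 | 398 | 728 |
| 50 | 1.2 | 430 | 405 | 247 |

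**Step 4, a range of b.** Take a patient whose true corrected QT is 400 msec, so QT = 400·RR^b. The correct form returns 400 msec in every cell. The written form returns (msec):

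| HR (bpm) | b = 0.25 | b = 1/3 | b = 0.40 | b = 0.50 |
|---|---|---|---|---|
| 50 | 202 | 246 | 273 | 304 |
| 60 | 400 | 400 | 400 | 400 |
| 65 | 540 | 495 | 473 | 451 |
| 75 | 924 | 725 | 639 | 559 |
| 80 | 1,177 | 861 | 732 | 616 |
| 100 | 2,716 | 1,562 | 1,169 | 861 |

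The forms agree at 60 bpm, where RR = 1. At 65 bpm the error is already +51 to +140 msec. A rise from 75 to 80 bpm with no true change gives a false increase of 861.4 − 725.2 = 136 msec at b = 1/3, and of 615.8 − 559.0 = 57 msec at b = 0.50.

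**Step 5, a simulated distribution.** 20,000 readings per value of b were drawn with heart rate 80 ± 12 bpm, true corrected QT around 400 msec and 4% noise (all assumed); b was then re-estimated by the SAP's regression.

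| b | Correlation of QTcF with RR | Correlation of written QTcS with RR | Mean written QTcS (msec) | Written QTcS >500 msec |
|---|---|---|---|---|
| 0.25 | −0.31 | −0.88 | 1,313 | 91% |
| 1/3 | 0.00 | −0.92 | 904 | 89% |
| 0.40 | 0.25 | −0.94 | 748 | 87% |
| 0.50 | 0.54 | −0.95 | 622 | 81% |

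With QT/RR^b the correlation is about 0, the mean about 400 msec, and no value exceeds 500 msec. When b is close to 1/3, QTcF is already free of RR and QTcS would not be called for. The rows away from 1/3 are the ones where QTcS would be derived, and the error is large in all of them.

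**The case against.** The algebra is not in dispute; the case on the other side is about consequence.

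- **QTcS is supplementary and conditional.** It needs a residual correlation and enough participants with baseline ECGs (eg, more than 30). QTcB and QTcF are reported in any event, so real prolongation would still show in those tables. This stands. The count condition is easily met, with 44 patients planned and triplicate screening ECGs required in all of them. The documents do not say how likely the correlation condition is.
- **No clinical rule uses QTcS.** Eligibility, redosing and the protocol's QT event of special interest use QTcF (the last alongside toxicity grade), and the SAP's own list of such events has no QT item. This stands: the harm is confined to reporting.
- **Only the absolute-value categories name QTcS.** The list of maximum increases (>30 and >60 msec) names no particular correction. That QTcS would also feed those increases is a reasonable reading, not an explicit statement.
- **The error is conspicuous.** Values above 1,000 msec beside normal QTcF would probably be noticed. That is likely for fast rates, less so for moderate shifts near 60 bpm, and a prespecified formula should not depend on someone noticing.
- **The exponent could be a text-extraction error.** The expression reads as intact and nothing suggests damage, but a check against the source PDF is sensible.

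**Conclusion.** The formula is wrong as written. It contradicts the regression that defines b, the SAP's Fridericia and Bazett formulas, and the section's stated aim of a value independent of heart rate. The result follows from algebra and needs no assumption; it fails only at RR = 1 s or |b| = 1, where the two forms coincide.

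The size does rest on assumptions. For b between 0.25 and 0.50 and a true corrected QT of 400 msec, the written value is 559 to 924 msec at 75 bpm and 202 to 304 msec at 50 bpm. The consequence is limited to the conditional QTcS summaries: the maximum on-treatment category table for certain, and probably the shift and maximum-increase tables. The fixed corrections, the clinical rules and the test of CR/CRi are untouched. It should be corrected before the ECG programs are finalised.

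**What to change.** In SAP 6.6.5, change the derivation to QTcS = QT(msec) / (RR(sec))^b and make the same change in the programming specification. Keeping 1/b and redefining b as the reciprocal of the slope is equivalent, but less clear.

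While editing, state which ECGs the regression uses. The condition for deriving QTcS refers to baseline ECGs, but the regression step does not name its data; one phrase saying that b is estimated from baseline ECGs would settle it. As a programming check, b = 1/3 must reproduce QTcF and b = 1/2 must reproduce QTcB.

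The cost is one symbol and one phrase. No new data are needed, and there is no effect on sample size, the primary analysis or the other QT summaries. Confirm the exponent against the source PDF first.

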6.6.6. Physical Examination

Physical examination, as applicable, collected during the course of the study will be considered source data and will not be required to be reported, unless otherwise noted. However, any untoward findings identified on physical and/or neurological examinations conducted during the active collection period will be captured as AEs, if those findings meet the definition of an AE.

7. INTERIM ANALYSES

Not applicable.

8. APPENDICES

8.1. Appendix 1. Outcome Definitions

The below outcome definitions will be used for reporting of disease assessments:

- Complete response (CR) is defined as a disappearance of leukemia as indicated by <5% marrow blasts and the absence of peripheral blood leukemic blasts, with recovery of hematopoiesis defined by absolute neutrophil count (ANC) $\geq 1000/\mu\text{l}$ and platelets $\geq 100,000/\mu\text{l}$. C1 extramedullary disease status is required.

Extramedullary disease status:

- C1: Complete disappearance of all measurable and non-measurable extramedullary disease with the exception of lesions for which the following must be true: For participants with at least one measurable lesion, all nodal masses >1.5 cm in greatest transverse diameter (GTD) at baseline must have regressed to ≤ 1.5 cm in GTD and all nodal masses ≥ 1 cm and ≤ 1.5 cm in GTD at baseline must have regressed to <1 cm GTD or they must have reduced by 75% in sum of products of greatest diameters (SPD). No new lesions. Spleen and other previously enlarged organs must have regressed in size and must not be palpable. All disease must be assessed using the same technique as at baseline.
- C2: Participant does not qualify for C1 status.
- Complete response with incomplete count recovery (CRi) is defined as CR except with absolute neutrophil count (ANC) $< 1000/\mu\text{l}$ and/or platelets $< 100,000/\mu\text{l}$.
- Partial response (PR) is defined as an improved or no worsening of ALL as indicated by no peripheral blood blasts, neutrophils $\geq 1000/\mu\text{l}$, platelets $\geq 100,000/\mu\text{l}$, and either or both of the following:
 - At least a 50% decrease in the marrow blast percentage, compared to the pretreatment value, and marrow blast percentage $\geq 5\%$ and $\leq 25\%$.
 - C2 extramedullary disease status.
- Treatment failures are defined as participants who fail to achieve CR, CRi or PR will be classified according to the type of failure:
 - Resistant disease: Participant survives ≥ 7 days following completion of initial treatment course and has persistent leukemia in the most recent peripheral blood smear or bone marrow and/or persistent disease involvement at any extramedullary site after completion of therapy.
 - Death during aplasia: Participant survives ≥ 7 days following completion of initial treatment course then dies while cytopenic, with the last post-induction bone marrow without leukemic blasts.

- Indeterminate:
 - Participant survives <7 days after completion of initial treatment course.
 - Participant survives ≥ 7 days following completion of initial treatment course then dies with no persistent leukemia in the peripheral smear but no post-induction bone marrow examination or extramedullary disease examination.
- Relapse from CR or CRI:
 - Appearance of leukemic blasts in the peripheral blood.
 - Appearance of extramedullary disease.
 - $\geq 5\%$ blasts in the bone marrow not attributable to another cause (eg, recovery of normal cells following chemotherapy-induced aplasia). If there are no circulating blasts and no extramedullary disease and the bone marrow blast percentage is $\geq 5\%$ but $<20\%$, then a repeat bone marrow performed at least 7 days after the first marrow examination and documenting bone marrow blast percentage is 5% is necessary to establish relapse.
- Progressive disease (PD) is defined as a doubling of peripheral blasts with an absolute increase of $>5 \times 10^9/L$ and/or appearance of or progression of extramedullary disease.

The following criteria will be used for evaluation of extramedullary disease:

- Measurable extramedullary disease: Lesions that can be accurately measured in two dimensions by CT, MRI, medical photograph (skin or oral lesion), or other conventional technique and a greatest transverse diameter of 1 cm or greater; or palpable lesions with both diameters ≥ 2 cm. Note: although CT scans remain the standard for evaluation of nodal disease, radiographic scans are not required for participants with easily palpable/superficial nodes.
- Non-measurable extramedullary disease: All other lesions including unidimensional lesions, lesions too small to be considered measurable, pleural or pericardial effusions, ascites, bone disease, leptomeningeal disease, lymphangitis, pulmonitis, abdominal masses not confirmed or followed by imaging techniques or disease documented by indirect evidence only (eg, lab values).

Modified from: Cheson et. al., Revised recommendations of the International Working Group for Diagnosis, Standardization of Response Criteria, Treatment Outcomes, and Reporting Standards for Therapeutic Trials in Acute Myeloid Leukemia. J Clin Oncol. 2003 Dec 15;21(24):4642-9.

8.2. Appendix 2. Definitions of Adverse Events of Special Interest

IMPORTANT IDENTIFIED RISKS

- Grade ≥ 3 hepatotoxicity and/or serious hepatotoxicity, including VOD/SOS.

GRADE ≥ 3 HEPATOTOXICITY AND/OR SERIOUS HEPATOTOXICITY, INCLUDING VOD/SOS AEs will be defined as:

- Grade ≥ 3 AEs and/or SAEs retrieved by applying the following MedDRA SMQs: Cholestasis and jaundice of hepatic origin (SMQs narrow); Hepatic failure, fibrosis, cirrhosis, and other liver damage related conditions (SMQs narrow); Hepatitis, noninfections (SMQs narrow); Liver related investigations signs and symptoms (SMQs narrow and broad);
- Grade ≥ 3 AEs and/or SAEs encoded to the following MedDRA PTs: Hepatic vein occlusion, Hepatic vein thrombosis, Portal vein thrombosis, Budd-Chiari Syndrome, Chronic graft-versus-host disease in liver, and Acute graft-versus-host disease in liver;
- All AEs encoded to the following MedDRA PTs: Venoocclusive liver disease and Venoocclusive disease.
- Myelosuppression/cytopenia.

MYELOSUPPRESSION/CYTOPENIA AEs will be defined as:

- Any reported PTs retrieved by applying the following MedDRA SMQs: Haematopoietic thrombocytopenia (SMQ narrow and broad), Haematopoietic leukopenia (SMQ narrow), Haematopoietic erythropenia (SMQ narrow and broad), and Haematopoietic cytopenias affecting more than one type of blood cell (SMQ narrow).

INFECTION AEs (not considered a separate risk, but considered to be complications of myelosuppression/cytopenia) will be defined as:

- Any reported PTs retrieved by applying the MedDRA SOC: Infections and Infestations.

HAEMORRHAGE AEs (not considered a separate risk, but considered to be complications of myelosuppression/cytopenia) will be defined as:

- Any reported PTs retrieved by applying the MedDRA SMQ: Haemorrhage terms (excluding laboratory terms) (SMQ narrow).

IMPORTANT POTENTIAL RISKS

- Interstitial lung disease (ILD).

INTERSTITIAL LUNG DISEASE AEs will be defined as:

- Any reported PTs retrieved by applying the MedDRA SMQ: Interstitial lung disease (SMQ narrow);
- All AEs encoded to the following MedDRA PT: Graft versus host disease in lung.
- Inflammatory gastrointestinal events.

INFLAMMATORY GASTROINTESTINAL EVENT AEs will be defined as:

- Any reported PTs retrieved by applying the MedDRA Version SMQ Gastrointestinal nonspecific inflammation (SMQ narrow);
- All AEs retrieved by applying the MedDRA higher level term (HLT) Colitis (excluding infective) (all paths) and Stomatitis and ulceration (all paths);
- All AEs encoded to the following MedDRA PTs: Oral pain, Oropharyngeal pain, and Mucosal inflammation.
- Pancreatitis

PANCREATITIS AEs will be defined as:

- Any reported PTs retrieved by applying the MedDRA Version SMQ: Acute pancreatitis (SMQ narrow);
- All AEs encoded to the following MedDRA PTs: Amylase abnormal, Amylase creatinine clearance ratio abnormal, Amylase increased, Lipase abnormal, Lipase increased, Lipase urine increased, Pancreatic enzyme abnormality, Pancreatic enzymes abnormal, and Pancreatic enzymes increased.
- Second primary malignancy.

SECONDARY PRIMARY MALIGNANCY AEs will be defined as:

- Any reported PTs retrieved by applying the MedDRA SOC: Neoplasms benign, malignant and unspecified (including cysts and polyps).

- Reproductive and developmental toxicity (post exposure during pregnancy and while breast feeding).

REPRODUCTIVE AND DEVELOPMENT TOXICITY AEs will be defined as:

- Any reported PTs retrieved by applying the following MedDRA SMQs: Termination of pregnancy and risk of abortion (SMQ narrow), Fertility disorders (SMQ narrow and broad), Foetal disorders (SMQ narrow and broad), Neonatal disorders (SMQ narrow and broad), Congenital, familial, and genetic disorders (SMQ narrow);
- All AEs encoded to the following MedDRA PTs: Pregnancy of partner, Exposure via father, Foetal exposure during pregnancy, and Maternal exposure during pregnancy.
- Nephrotoxicity.

NEPHROTOXICITY AEs will be defined as:

- Any reported PTs retrieved by applying the following MedDRA SMQ: Acute renal failure (SMQ narrow and broad).
- Neurotoxicity.

NEUROTOXICITY AEs will be defined as:

- Any reported PTs retrieved by applying the following MedDRA SMQs: Demyelination (SMQ narrow and broad) and Peripheral neuropathy (SMQ narrow and broad) and by searching for the following specific PTs under the higher level term: Cranial nerve disorders NEC (all paths).
